There may be some cost to participate in this study. Participants in the SB-TEAM group will be responsible to purchase each medication and spacer that is dispensed as part of this study as well as any fees associated with telemedicine visits (e.g., co-pays etc.) completed through the study (these are medical processes that should occur according to the national guidelines regardless of the child's participation in the study). Based on our prior work with this population, we anticipate that most of the children will have some form of health insurance to cover the cost of visits and the medications with minimal or no co-pay fee. In our prior studies we found that approximately 70% of families in the RCSD were insured with Medicaid which often eliminates co-pay fees for medications and care. If a child (in either group) does not have insurance, the study team will help the family secure health insurance. If a child in the SB-TEAM group is unable to obtain health insurance, the study team will pay for the participant's medication and spacer for the program. If there is no insurance reimbursement for the telemedicine visit, subjects will not be asked to pay any additional costs. Participants and their insurance company will be responsible for the cost of all standard of care office visits and additional medications prescribed by their PCP.

7. Data Storage and Confidentiality

To maintain the integrity, security, and confidentiality of study data, the data will be maintained in a secure and encrypted web-based database and/or a password protected database on a secure university network drive. No subject data will be stored on the internal hard drives of any Strong Health computers. After data validation and analysis, subject information will be de-identified. All consent

forms, paper surveys and additional correspondence will be stored in a locked filing cabinet in a locked hallway or locked office, and will only be accessible by the study staff.

Baseline, follow-up, and chart review data will be entered into a password-protected Microsoft Access database. This database is stored on a secure university network drive that is only accessible by the research team whom must use their NetID and password to access the database. Data may also be collected using RedCap, a secure, password protected database (using University NetID's and passwords) hosted through the University of Rochester.

The screening data and PCP reports will be entered and/or generated through a secure password-protected website created and managed by SophiTEC, a consulting and web design company that manages several web applications for the Rochester City School District and other clinical research projects. RCSD school nurses and the nurses or health advocates at Wilson Commencement Park, Ibero and the Volunteer's of America will have limited access to the web-based system to edit or review information for only the children/participants in their care. Study personnel and school nurses will each have their own unique login to the system. SophiTEC will manage and maintain study data backups. The web application will utilize high grade encryption, and prior to any internet transmission, the webpage will be encrypted. Timeout systems will also be in place to expire viewing data on the webpage.

Portions of the final assessments with caregivers, nurses, and healthcare providers may be tape recorded. These recordings will be saved on a university network drive that is only accessible by study personnel whom must use their NetID and password to access these tape recordings. Once the recordings have been transcribed, they will be deleted from the network drive.

The Rochester City School District has partnered with the University of Rochester study team for this study, and all of the procedures follow the school district's rules of privacy and confidentiality, as outlined in the letter from [name], Chief of Accountability for the Rochester City School District. As deputies of the school district, the study team is granted permission to review limited student information and contact families to inquire about their willingness to participate in the study.

8. Safety

This is *not* a drug investigational study since the effectiveness and safety of the FDA approved drugs that will be authorized/prescribed are already established and are not being tested. The intervention proposed should pose minimal risk to the children, since the medications that will be delivered at school for the children in the intervention group are medications that are recommended as the standard of care for children with the degree of asthma symptom severity required for enrollment into the program and are prescribed at the discretion of a pediatric health care provider. The most common side effects of inhaled corticosteroids, including yeast infection of the mouth and facial rash, will be assessed during each follow-up interview and during the telemedicine assessments. All children will be instructed to rinse their mouth with water after each dose of medication to prevent these side effects. Any significant concerns will be relayed promptly to the study coordinator, the principal investigator, the child's primary care provider, the study DSMB, and the Research Subject's Review Board. There is a potential but small risk of adverse effects on linear growth from the use of inhaled steroids; however, this risk is felt to be outweighed by the benefits for children with persistent asthma. In general, these medications are well tolerated and safe, and most studies do *not* demonstrate a negative effect on growth with moderate dosages of inhaled corticosteroids, that will be used in this study. The frequency and severity of all reported adverse events will be systematically recorded. Assessment of potential adverse effects will be completed at each telemedicine visit and telephone interviewers will inquire about any adverse

events, and specifically ask about any yeast infections of the mouth and facial rash. Any child (in either group) experiencing an acute asthma exacerbation at the time of a home visit or follow-up phone call will be referred immediately to their primary care provider for care. In addition, school nurses will be instructed to contact the parent of any child presenting to the nurses office with acute symptoms and refer them promptly to their primary care provider.

At home visits, research assistants will make efforts to protect subject privacy and confidentiality. The research assistants will assure that the subject is comfortable answering questions and discussing the study prior to completion of consent or any study measures. If it is suspected that someone in the home may cause serious harm to themselves or others, the study team will report these issues to the study coordinator and the principal investigator who may be mandated to report these concerns to appropriate authorities. There is also a risk that the study team may discover an unknown medical condition. If this is to occur, we will refer the family to their PCP or another appropriate health care professional for evaluation and treatment.

The study team will receive safety training yearly from key study personnel and safety plans for home visits will be created (including traveling in pairs, safe words for emergency situations, and procedures for notifying and updating coordinators about whereabouts). Additionally, these procedures are outlined in a team training manual given to all employees. The study team will also receive cultural awareness training from key study personnel prior to completing home visits.

Data Safety Monitoring Plan (DSMP):

This study also includes a Data Safety Monitoring Plan as submitted to and approved by the study sponsor: National Institutes of Health and National Heart, Lung, and Blood Institute. A formal Data Safety and Monitoring Board has been assembled for this project. The plan for safety and monitoring is as follows.

9. Data and Safety Monitoring

Data Quality Monitoring

The research associates will be responsible for all data collected during the home assessments. They will receive training from key study personnel regarding asthma terminology, symptoms, medication understanding, and environmental assessment. They also will be trained by the senior project coordinator on the use of equipment for cotinine measurements and the NIOX MINO[®] instrument for collection of exhaled nitric oxide.

The senior project coordinator and project coordinators are all experienced in asthma terminology, symptoms and other aspects of the illness and have extensive training in research methods. They will oversee the data collection methods and all data will be reviewed by the study coordinators. Data forms will be completed at each study home visit or telephone interview and will be returned with a cover sheet and other source documentation support materials (informed consent, contact information, etc.). Pre-intervention training of study staff will be conducted to increase knowledge about asthma, asthma medications, and other important information in order to reduce the number of “real-time” data collection errors. Through this training, staff will note any inconsistencies in parent reported data and will discuss them with the parent at the time of the interview.

Key study personnel will perform all follow-up interviews and follow-up data management. These data will be collected by the follow-up research associates who are independent from the research associate recruiters, and thus we will be able to perform blinded assessments of outcomes. Our team, including the principal investigator, senior project coordinator, and recruitment and follow-up project

coordinators, have a prior record of high-quality data collection and management. We tracked over 500 children in our prior school-based randomized trial, and completed follow-ups with 93% of subjects. Treatment group assignment will not be included with any follow-up materials in order to ensure blinding of the outcome assessment.

Once forms have been collected, errors that can be corrected over the telephone (legibility, incorrect dates, etc.) will be done using telephone interviews. Forms will be keypunched into the database using a double-entry system technique and checklists will be used to ensure that all data forms have been received and entered into the database. Simple range checks as well as cross-form validation checks will be performed to ensure the accuracy and completeness of the data. A list of all data checks performed will be maintained and any errors detected by this method will be noted on the form in red ink (initials and date of change). In addition, data forms, valid informed consent documents for each enrolled patient, and supporting source documentation materials will be reviewed by the research associates for accuracy. Required regulatory documents (IRB approval, updates to the protocol, data monitoring documents) will be maintained by the senior study coordinator. All events during the course of the trial including study enrollments, adverse events and study terminations will be reported to the senior study coordinator.

Safety Monitoring Plan

A Data Safety Monitoring Board (DSMB) including a pulmonologist ([name]; Division of Pediatric Pulmonology, University of California Los Angeles), a general pediatrician and health services researcher ([name], MPH; Division of General Pediatrics, Children's Memorial Hospital at Northwestern University), and a human subjects specialist ([name], MS, MPA; Department of Pediatrics, University of Rochester), has been assembled to provide ongoing oversight of the study. The DSMB will meet bi-annually or more frequently as needed to review study procedures and data. Potential risks related to participation in this study are minimal since the medications delivered through this program are routinely recommended by national guidelines for asthma care. In our previous school-based asthma program, which included 530 children, there were no reports of significant adverse events. The frequency and severity of all reported adverse events will be systematically recorded at each follow-up interview. Telephone interviewers will inquire about any adverse events, and specifically ask about any yeast infections of the mouth and facial rash. Any significant adverse events will be flagged by the follow-up research associates and relayed promptly to the senior study coordinator, the principal investigator, the child's primary care provider, the Institutional Review Board, the DSMB, and the NIH within 24 hours. We will hold bi-weekly research review meetings with the study team to provide an additional layer of monitoring to ensure subject safety as well as treatment integrity.

If a caregiver reports significant depressive symptoms or unusual circumstances (i.e., difficulty providing food or shelter for the family), we will offer the caregiver mental health or community resources and encourage the caregiver to contact their physician, a resource, or other trusted party. We will also offer to have a research nurse call the caregiver and provide additional support, if needed. The research nurse, trained in mental health counseling, will also determine if there are any immediate needs of the family and will advise the family and research team on next steps.

All records will be kept strictly confidential as required by the policies and procedures of the University of Rochester where data are collected, processed, or reported.

10. Potential Benefits

Potential benefits for participants of the randomized trial exist for both groups of children (SB-TEAM and eUC). The goal is for children in the SB-TEAM group to have improved symptom assessment, adherence

to preventive medications, and appropriate tailoring of therapy, thus they may experience less morbidity from asthma. Although children in the eUC group will not be receiving medication through school or telemedicine asthma visits, we will prompt their PCP to provide guideline based asthma care including prescription of the appropriate preventive medications and will provide regular reminders to PCPs and caregivers to care for the child's asthma. Improved asthma management should result in reduced morbidity for these children. Since the medications used in this study are safe and effective at the doses administered, and are strongly recommended by the national asthma guidelines, we anticipate that the intervention benefits will outweigh the minimal risk of participation.

11. Analysis

Sample Size:

This study is designed to have adequate power to detect the smallest clinically significant difference in mean SFDs post-intervention between the intervention and enhanced usual care groups. Based on our previous data, we estimate the pooled standard deviation of SFD at 2.8 and within-subject correlation at 0.3. Power was calculated for the intervention effect on SFD with at least two assessments for each subject. We anticipate <15% attrition, as attrition was minimal (<10%) in the prior study, and therefore plan to enroll 400 children. With a final sample of 336, we will have 90% power to detect a difference of 0.8 symptom-free days or greater per 2-wk. period. This difference is supported by our prior data, and would justify continuing the intervention. There are more than 11,000 students in pre-k through 4th grade in the RCSD and at least 6,600 entering kindergarteners in a 3 year period. Conservatively assuming an asthma prevalence of 9%, more than 1,584 students have asthma, and approximately ½ of these students (792) have persistent asthma. In our prior study, we enrolled 74% of eligible subjects. A conservative estimate would allow us to enroll 120 subjects/year (60%), which is more than adequate to meet our sample size.

Primary Analysis:

The primary analysis of this study aims to assess the effectiveness of the SB-TEAM intervention in reducing asthma morbidity (including symptom-free days post-intervention (follow-ups at 4 mo, 6mo and final) as the primary outcome) compared to an enhanced usual care comparison group in school age children with persistent asthma. We will follow subjects prospectively throughout the school year for clinical outcomes (symptoms, asthma control, health care use), functional outcomes (absenteeism, quality of life), and airway inflammation (FeNO). We will use graphical and numerical summaries to describe the outcomes at each assessment point. If distributional assumptions associated with a particular statistical procedure are violated, appropriate transformations will be made or non-parametric alternatives will be used. In accordance with the intention-to-treat principle, all randomized subjects will be analyzed within the group to which they were assigned; minimal crossover is expected. Hypothesis-driven comparisons will be made to control the family-wise type I error rate at 0.05 (two-sided) for the primary hypothesis.

We will determine whether there are important differences at baseline despite randomization between the SB-TEAM and eUC groups in demographics and background characteristics (age, race, ethnicity, insurance, caretaker education), depression, and cotinine. This will include t-tests (or Wilcoxon Rank Sum test) for continuous variables and chi-square (or Fisher's Exact) tests for discrete variables. These comparisons will enable the identification of control variables for use in analyses evaluating treatment effect.

To test for differences between the SB-TEAM and eUC groups on clinical and functional outcomes at the primary time point, bivariate comparisons will be made using t-tests for continuous variables (number of symptom-free days (SFD), symptom nights, rescue medication use, days absent, quality of life, FeNO,

and ACT scores), and chi-square tests for discrete variables (acute visits, hospitalizations). In addition, the time-course of treatment response during the follow-up period will be evaluated using a linear mixed model with the primary outcome, SFD at post-intervention, as the response, and treatment condition, treatment by time interaction as independent variables. We will model the repeated assessment post-intervention and assess post treatment effects as well as maintenance gain during the period using appropriate linear contrasts. The analysis will be controlled for baseline symptoms, and variables that are found to differentiate between groups at baseline. The treatment effect will be regarded as fixed and the subjects will be modeled as random effect, with an appropriate variance covariance structure specified. Secondary continuous outcomes will be analyzed in a similar manner. Discrete outcomes will be analyzed by fitting Generalized Estimating Equation model. Appropriate link functions and response probability distributions will be specified.

We will also consider whether certain process measures from our conceptual framework (adherence, patient/provider communication, satisfaction with medical care) act as mediators in the relationship between the intervention and outcomes. Thus we will estimate both the direct intervention effect on the outcomes, as well as the indirect effect through process mediators. For each purported mediator, we will use structural equation models (SEM) to model its relationship to treatment and primary outcome. SEM can quantify both direct relationships between latent traits, the effects of factors that modify these relationships, and also indirect relationships mediated by other factors. Potential confounders such as baseline symptoms will be included as covariates. Maximum Likelihood (ML) will be used for estimation. Goodness-of-fit will be assessed in a two-level process. In the first level, the fit of the unrestricted model will be tested using standard diagnostic measures for linear regression. In level two, the appropriateness of assumption of the proposed structural equation model will be investigated by testing this model against the unrestricted model. The following indicators will be used: (a) Comparative Fit Index (CFI), (b) Non-Normed Fit Index and (c) Root Mean Square Error of Approximation. We will use chi-square statistics for the structural invariance tests to determine effect modifiers. These analyses will aid in our understanding of pathways by which SB-TEAM impacts outcomes.

The primary analyses will be performed according to the intention-to-treat principle and will include all randomized subjects. Substantial attention will be invested in participant retention; reasons for any subject withdrawals that may occur will be carefully documented. Missing data patterns will be examined by comparing subjects who discontinued with those who remained in the study. Inference based on the proposed methods GEE and/or LMM is valid provided that missing data follows the missing completely at random (MCAR) assumption. However, if the occurrence of missing data depends on the observed response but is independent of unobserved data (MAR), weight GEE (WGEE) will be used. Sensitivity analysis to MAR assumption will also be carried out.

Cost Effectiveness Analysis: *Establish the cost-effectiveness of the intervention with a specific focus on ultimate sustainability and dissemination.* We will assess health and economic benefits of SB-TEAM from both the societal and the Medicaid perspective. We also will use *Diffusion of Innovations Theory* to help understand how this innovative model can be maintained in the current system of care through city schools.

We will assess health and economic benefits of SB-TEAM compared to enhanced usual care by using cost-effectiveness (CE) methodology. The time horizon of the study will be one school year (September-June). Four cohorts that will complete the study in consecutive years will be analyzed as one stacked study cohort. The basecase analysis will be conducted from the societal perspective which includes all identifiable costs and benefits, regardless of whom they impact. The majority of children in the study

are eligible for Medicaid (73% based on the prior study), thus a second analysis will take the Medicaid perspective. The benefits of the intervention will be measured as the number of symptom-free days during the school year.

Three main categories of costs to be considered include programmatic costs, productivity costs, and medical costs estimated at the individual child level. Programmatic costs include costs of initiating and running the program, hiring and training staff, purchasing or leasing equipment, staff travel, and information system costs. Costs associated with this study that would not exist as part of the intervention will not be included, as we do not anticipate that they would continue beyond the duration of the study. Per person programmatic costs will be calculated by dividing the total costs of the program by the total number of children with persistent asthma in the schools. We will determine *productivity/opportunity costs* based on the amount of time parents take from work to care for sick children or take them to a doctor. Time from work will be valued at the median of the pay scale estimates based on age, race and gender specific wages from the Bureau of Labor Statistics. We will assess the impact of the intervention on *medical* costs using parent-reported health services use data and medical record review. We will ask parents at each follow-up about their child's ER or physician visits, hospitalizations, medical procedures, use of medications and durable equipment. Healthcare use will be converted to costs using the NYS Medicaid fee schedule and other sources. Annual medical costs per person will be analyzed using a 2-part model to adjust for zero expenses in a given year. All costs will be adjusted to the last year of the intervention using the appropriate component of the Consumer Price Index (CPI).

We will consider the total costs of initiating and maintaining the program as well as the incremental cost-effectiveness ratio (ICER) of the SB-TEAM vs. eUC, which is the ratio of differences in costs between the 2 study groups to the difference in the number of symptom-free days (SFD) gained between the 2 groups. The main outcome for the analysis from the societal perspective will be an incremental cost-effectiveness ratio (ICER), which is the ratio of net program costs to the number of symptom-free days (SFD) gained, $ICER = (\Delta Medical + \Delta Productivity + \$Program) / \Delta SFD$, where $\Delta = (SB-TEAM) - (eUC)$. We will bootstrap the ICER to estimate standard error and to evaluate the uncertainty around the point estimate. The ICER will be compared to similar estimates from the literature. An acceptability curve, linking various values of 1 SFD to the probability of SB-TEAM being cost-effective, will be plotted. The study from the Medicaid perspective will use the cost-benefit approach to economic evaluation. Benefits will be described as the net difference in medical and productivity costs between children in the SB-TEAM and eUC groups. The cost is equivalent to the cost of the program. Equation: *Net Monetary Benefit* = $\Delta Medical - \$Program$.

Process Evaluation: Descriptive statistics will be used for the process evaluation, looking in particular at the efficiency of the program implementation along with the responses from parents, primary care providers, and school nurses and administrators about convenience, scheduling, satisfaction, and sustainability.

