triggers (collected at screening) into the system, and will upload the physical examination including medical images, height/weight, breath sounds, and spirometry measurements (if a spirometer is available and the child is able to perform this test). This visit information will be securely stored in the telemedicine system's "virtual waiting room" until a provider is ready to complete the visit (visits do not need to be completed in 'real time'). Using the scheduling system pre-established by the telemedicine program and coordinated with the medical practices that provide telemedicine visits, a provider will be notified that a child's visit is available in the "virtual waiting room". The provider will log on to the telemedicine system from their office and perform the visit by reviewing the symptom information collected, viewing the child's images, and listening to the breath sounds. The telemedicine provider will then contact the child's caregiver via telephone to further discuss the child's asthma and develop a treatment plan. The telemedicine provider will deliver brief asthma education (eg; trigger avoidance, symptom monitoring) and referrals to community resources as needed, and will send a guideline-based preventive medication prescription electronically to a local pharmacy through the telemedicine system. After the visit, a summary of the assessment and treatment plan will be sent to the parent (through the school) and faxed through the system to the child's PCP for inclusion in the medical record. The telemedicine assessment at school will approximate care that would be delivered at an outpatient asthma visit and will use a standard asthma visit template; visits take approx. 20 minutes. Reimbursement will be submitted to the child's health insurance, similar to a standard asthma visit (Rochester payers reimburse for telemedicine visits).

Several clinicians routinely perform telemedicine visits as part of our current system, through 4 different practices that serve >60% of the children living in the city of Rochester. We will schedule asthma visits with the child's primary care practice when possible. If there is no telemedicine provider at the child's practice (or if the provider is unavailable for the visit), several providers are routinely available to perform visits; this scheduling system is well received and works very efficiently.

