Although children may use any FDA approved daily preventive asthma medication as part of this study, we anticipate that most children will be using Flovent®, Advair® or Pulmicort® as these are the most common asthma medications used in Rochester.

Examples of medications and doses that likely will be prescribed for this study:

Flovent® 110 mcg, 2 puffs, once a day

Advair® 250/50 mcg diskus (DPI), 1 inhalation, once a day

Advair® 115/21mcg inhaler, 2 puffs, once a day

Pulmicort® 180 mcg Flexhaler (DPI), 2 inhalations, once a day

After each telemedicine visit, the asthma coordinator will carefully review each child’s asthma medication and dose, and will assure that appropriate preventive medications has been prescribed according to NHLBI guidelines.

Follow-Up Telemedicine Asthma Control Assessments and Medication Adjustments– Follow-up telemedicine assessments will occur twice during the study period. Follow-up visits will be scheduled at school 4-6 weeks after initiating DOT, and again 4-6 weeks later. These visits will focus on assessment of control, assessment of ongoing triggers or co-morbid conditions that might interfere with an optimal response to treatment, and brief asthma education. The telemedicine provider will also assess for any medication-related side effects (oral thrush, growth monitoring). Guideline-based medication adjustments (or specialist referral, if appropriate) will be recommended for children who continue to have persistent symptoms despite DOT in school. Information regarding changes in the child’s regimen will be discussed with caregivers and reports will be sent to the PCP.

We do not anticipate the opportunity to step-down therapy, since all children will have persistent symptoms at the start of the trial and could benefit from several months of anti-inflammatory therapy. A natural time for discontinuing or stepping-down therapy occurs at the end of the school year when the children will no longer be receiving medications through school. Two weeks prior to the close of the study, we will notify both PCPs and families that children receiving preventive medications at school no longer will receive medications through the study. PCPs will be directed to provide ongoing medication management as needed.

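### Side effects are sought by two routes, one of them open only to SB-TEAM, and the plan does not say which route feeds any by-arm adverse-event count

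*Combined protocol and SAP*

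**What the plan says.** All references are to the combined protocol and SAP.

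- **Two routes of enquiry.** Section 8 (Safety) says that the common inhaled-steroid side effects "will be assessed during each follow-up interview and during the telemedicine assessments". Later in the same section: "Assessment of potential adverse effects will be completed at each telemedicine visit and telephone interviewers will inquire". It also promises that reported adverse events will be recorded with their frequency and severity, without limiting the source.
- **One route of recording.** The Safety Monitoring Plan in section 9 says: "The frequency and severity of all reported adverse events will be systematically recorded at each follow-up interview". It does not mention telemedicine.
- **Routing.** Data Quality Monitoring in section 9 sends adverse events to the senior study coordinator and mentions no source label.
- **Who has which route.** Section 4 (Follow-Up Assessments) gives caregivers in both arms a call every other month from blinded research assistants, then a final home visit. Telemedicine belongs to SB-TEAM: "Follow-up telemedicine assessments will occur twice during the study period", after an initial visit. Section 10 confirms the contrast: "Although children in the eUC group will not be receiving medication through school or telemedicine asthma visits". The eUC contacts at matching intervals (section 3, part B) are prompts about care, with no side-effect enquiry stated.
- **Growth.** At the telemedicine visit the assistant "will upload the physical examination including medical images, height/weight, breath sounds", and growth is named among the things to be checked at telemedicine follow-up. The table in section 5 (Measures) lists no growth measure for either arm.
- **Analysis.** Section 11 sets out no between-arm safety analysis.

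**The concern.** A side effect can be counted only if someone looks for it. SB-TEAM children are looked at more often than eUC children, and the extra looks are made by a clinician who has an uploaded examination and knows the child is in the intervention. A data manager following section 8 and the routing rule could reasonably put every event into one file. One following the Safety Monitoring Plan could reasonably enter interview events only. The first file would tend to show an SB-TEAM excess of thrush and rash that reflects detection and not harm.

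The DSMB meets twice a year to review study data, and the final report will presumably describe adverse events. If either sees pooled counts by arm, part of any difference would be an artefact whose size could not be recovered later without a source label.

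**Working it through.** **Enquiry points per child.** Section 6 (Compensation) pays $20 at baseline, $20 per telephone survey and $50 at the final survey, with a cap of $130. Telephone surveys: (130 − 20 − 50) / 20 = 3. With the final survey that makes 4 interviews in each arm, which agrees with calls every other month and the 4-month, 6-month and final time points in section 11. SB-TEAM adds 2 telemedicine follow-ups, or 3 visits if the initial one counts. The totals are 6 to 7 against 4.

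**Effect of pooling.** The plan gives no adverse-event rate and no detection probability, so these inputs are assumptions:

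- p: true risk over the year, equal in both arms
- s: chance that the interviews elicit an event that occurred
- t: chance that the telemedicine visits find an event the interviews missed

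Observed rate in eUC = p·s. Observed rate in SB-TEAM with sources pooled = p·[1 − (1 − s)(1 − t)]. The ratio is therefore 1 + t(1 − s)/s, which does not depend on p.

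Example: s = 0.7, t = 0.3 gives 1 + 0.3 × 0.3 / 0.7 = 1.13.

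Expected cases among 200 per arm (the allocation in section 3) at p = 10%:

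| s | t | eUC | SB-TEAM, pooled | Ratio |
|---|---|---|---|---|
| 1.0 | any | 20.0 | 20.0 | 1.00 |
| 0.9 | 0.1 | 18.0 | 18.2 | 1.01 |
| 0.9 | 0.3 | 18.0 | 18.6 | 1.03 |
| 0.7 | 0.3 | 14.0 | 15.8 | 1.13 |
| 0.7 | 0.5 | 14.0 | 17.0 | 1.21 |
| 0.5 | 0.3 | 10.0 | 13.0 | 1.30 |
| 0.5 | 0.5 | 10.0 | 15.0 | 1.50 |

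With 200 per arm and a two-sided 5% test, the chance of a nominally significant SB-TEAM excess is about 18% in the last row and about 3% at s = 0.9, t = 0.3. With no artefact it would be 2.5% (half of 5%).

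**Interviews only.** The observed rate is p·s in both arms, so the expected ratio is 1.00 whatever s is, provided s is the same in both arms.

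**Growth.** Telemedicine follow-ups fall 4–6 weeks after directly observed therapy starts and again 4–6 weeks later. The last planned height is thus about 8–12 weeks into therapy, in follow-up of 7–9 months, and eUC has no planned height. No between-arm growth contrast can be formed.

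**Primary endpoint.** The sample size uses no safety input and reproduces. With two assessments, the effective SD is 2.8 × √((1 + 0.3)/2) = 2.257. A difference of 0.8 at 90% power and two-sided 0.05 then needs 168 per arm, 336 in all, as stated.

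**The case against.** The strongest reply is that the plan already holds a fair comparison. Interviewers are blinded, both arms follow one schedule, and every caregiver is asked about oral yeast infection and facial rash. The Safety Monitoring Plan ties recording to those interviews. Section 8 lists two routes of enquiry but never says they will be merged into one rate, and section 9 never says interviews are the only source, so the two are not in flat contradiction. No between-arm safety test is planned, and section 8 says drug safety is not under test. Any artefact would also run against the intervention.

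Most of that stands, and it rules out three stronger readings that a reader might infer:

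- **That adverse-event rates are not comparable by design.** They can be compared on the interview stream. The bias arises only if sources are pooled and shown by arm, which the documents neither state nor exclude.
- **That SB-TEAM would show an excess of about 43–49%.** This comes from treating each contact as an independent chance of a report: 1 − (1 − p)^6 against 1 − (1 − p)^4, where p is now an assumed 1% to 5% chance per contact. That ratio tends to 6/4 = 1.50 as p falls, so it mostly restates the visit count. It ignores that an event seen at telemedicine may also be reported at the next interview.
- **That growth will look worse in SB-TEAM.** Heights from one arm provide no comparator. They cannot make that arm look worse.

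What the reply does not remove is the missing rule. The common stream protects the comparison only if someone is told to use it, and without a source label the pooled file cannot be separated afterwards.

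**Conclusion.** The concern holds as a gap in specification. Section 8 and the Safety Monitoring Plan differ on where adverse events come from, and no text assigns a source to any by-arm count. If the routes are pooled, the artefact favours eUC. Its ratio is 1.00 to 1.50 over s from 0.5 to 1.0 and t from 0.1 to 0.5, and is close to 1 when interviews catch nearly everything. Those limits come from the assumed grid and are not bounds: a lower s would give a larger ratio. The calculation also assumes equal true risk in both arms and equal interview sensitivity.

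The primary endpoint and its sample size are untouched. On growth, the documents support only the statement that no between-arm conclusion is possible. They do not support requiring height measurement in both arms, which would add a procedure for something the plan does not list as an outcome.

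**What to change.** 1. Reconcile section 8 with the Safety Monitoring Plan in section 9, so that both name the same sources and say what each is used for.
2. Add a source field to the adverse-event record: follow-up interview, telemedicine visit, or both.
3. State that any adverse-event rate compared between arms, for the DSMB or the final report, counts only events elicited at the common blinded interviews.
4. List telemedicine-detected events in a separate SB-TEAM table, marked as having no comparator.
5. State that no between-arm growth conclusion will be drawn, because height is taken only at SB-TEAM telemedicine visits.

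The cost is one data field and a few sentences; no visit or measurement is added. There are two downsides. Events found only at telemedicine leave the comparative rate, although they are still reported and acted on. Some spillover may also remain: the telemedicine provider telephones the caregiver and a visit summary goes home, so a caregiver can repeat a telemedicine finding at interview. The source field would show how often an event was found by both routes.
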